## 8. EXTENT OF EXPOSURE AND TREATMENT COMPLIANCE

### 8.1 Exposure to Investigational Product

Exposure to IP will be summarised in terms of treatment duration for Parts 2 and 3, which is calculated as the number of days from the date of first dose of IP taken to the date of the last dose of IP taken within the respective part of the study, inclusively.

**Part 1:** Data regarding study drug exposure during Part 1 will be listed for the Safety Analysis Set 1, including treatment start date, treatment start time, and dose per administration (mg). **(Listing 5.1.1)** For the Safety Analysis Set 2, summary statistics (n, mean, standard deviation, minimum, median, and maximum) for the total daily dose (mg/day), and length of exposure (days) will be presented by treatment group where total dose is defined as the sum of the doses within a treatment group and total daily dose is defined as the total dose / total days of dosing. In addition, total exposure (person-years and a summary of the number (and percentage) of subjects who fall within the categories of  $\leq 1$  week,  $>1$ -2 weeks,  $>2$ -3 weeks,  $>3$ -4 weeks,  $>4$ -5 weeks,  $>5$ -6 weeks,  $>6$ -7 weeks,  $>7$ -8 weeks, and  $>8$  weeks, for the length of exposure will be presented by treatment group. Total exposure (person-years) will be the total number of days of IP (last dose – first dose + 1) summed over all subjects within a treatment group divided by 365.25 days. **(Table 4.1.1; Listing 5.1.2)**

**Part 2 and 3 Combined (Lanthanum carbonate only):** For the Safety Analysis Set 2 and SCS, summary statistics (n, mean, standard deviation, minimum, median, and maximum) for the total daily dose (mg/day), and length of exposure (days) will be presented. In addition, total exposure (person-years) and a summary of the number (and percentage) of subjects whose length of exposure fall within specified categories ( $\leq 1$  week,  $>1$ -4 weeks,  $>4$ -8 weeks,  $>8$ -12 weeks,  $>12$ -16 weeks,  $>16$ -20 weeks,  $>20$ -24 weeks,  $>24$ -28 weeks,  $>28$ -32 weeks, and  $>32$  weeks) will be presented. **(Table 4.1.2 and Table 4.1.3)**

Data regarding study drug exposure during Part 2 and 3 will be listed for the Safety Analysis Set 2 and SCS, including date of first dose, treatment, total daily dose (mg), and date of last dose. In addition the date the IP was returned from the previous visit, the amount of IP returned, the amount of IP taken, as well as the date the IP was dispensed, and the amount of IP dispensed, will also be listed by timepoint. **(Listing 5.1.2 and Listing 5.1.3, respectively)**

### 8.2 Measurement of Treatment Compliance

Investigational Product dosing compliance for a specified period is defined as the total number of sachets/tablets actually taken by a subject during that period divided by the number of sachets/tablets expected to be taken during the same period multiplied by 100. The total number of sachets/tablets actually taken is calculated by the total number of sachets/tablets dispensed minus the number of sachets/tablets returned. The number of sachets/tablets expected to be taken for a specified period is calculated as the number of days in that period multiplied by the number of sachets/tablets to be taken per day during that period. Within the summary tables of IP exposure, a summary of the number (and percentage) of subjects who fall within the compliance categories of  $<60\%$ ,  $60\% - 120\%$ , and  $>120\%$  will be presented. Exposure in Part 2 will be summarized by treatment group for Safety Analysis Set 2 **(Table 4.1.1)**; Lanthanum Carbonate

exposure in Part 2 and 3 combined will be summarized for the Safety Analysis Set 2 and SCS **(Table 4.1.2 and Table 4.1.3, respectively)**. Subject compliance within Part 1, Part 2 only and within Part 2 and 3 combined will be listed within the IP accountability listing by treatment group. **(Listing 5.1.1, Listing 5.1.2, Listing 5.1.3)**

## 9. PRIOR AND CONCOMITANT MEDICATION

Presently, version 2013Sep01\_DD (Basic) of the World Health Organization (WHO) drug dictionary, is being used to classify prior and concomitant medications by therapeutic class. However, nearer to the conclusion of data collection, a decision will be made as to the most desirable dictionary to use.

Prior medications will be presented for Part 1 (**Table 1.3.1**) and Part 2 (**Table 1.3.2**) and defined as any medication with a start date prior to the date of first IP intake in the relevant Part of the study, irrespective of when they stopped (for more specifics please see Protocol Section 5.1). Concomitant medication usage will be summarised by the number and proportion of subjects receiving each medication within each preferred term for the Safety Analysis Set 1, Safety Analysis Set 2 and the SCS.

**Part 1:** Concomitant medications in Part 1 are defined as any medication with a start date prior to Part 1 and continuing on to 2 days after the day of IP in Part 1. Concomitant medication usage will be summarised by the number and proportion of subjects receiving each medication within each preferred term for the Safety Analysis Set 1. Multiple medication usage by a subject in the same category will be counted only once. (**Table 1.3.3**)

**Part 2:** Concomitant medication in Part 2 of the study is defined as any medication with a start date prior to Part 2 and continuing after the first dose of IP in Part 2, or with a start date between the dates of the first and last doses of IP in Part 2, inclusive. **Any medication with a start date after the date of the last dose of IP in Part 2 will not be considered a concomitant medication in Part 2.** In the case of missing or partially missing start or stop dates for concomitant medications, if the information available could only lead to the medication being considered as starting on or after the first dose of IP in Part 2 and on or before the last dose date in Part 2 then it will be considered concomitant in Part 2. Concomitant medications will be listed and summarised by preferred drug name and treatment group. Concomitant medication usage will be summarised by the number and proportion of subjects in each treatment group receiving each medication within each preferred term for the Safety Analysis Set 2. Multiple medication usage by a subject in the same category will be counted only once. (**Table 1.3.4, Table 1.3.5**)

**Part 2 and 3 combined (Lanthanum carbonate only):** Concomitant medications in Part 2 and 3 combined are defined as any medication with a start date prior to and continuing after the first dose of lanthanum carbonate in Part 2 or 3, or with a start date between the dates of the first and last doses of lanthanum carbonate (inclusive) within Part 2 and 3 combined. Any medication with a start date after the date of the last dose of lanthanum carbonate in Part 2 and 3 combined will not be considered a concomitant medication in Part 2 and 3 combined. In the case of missing or partially missing start or stop medication dates, if with the available information one could only conclude that a medication started on or after the first dose of lanthanum carbonate in Part 2 or 3, and on or before the last dose of lanthanum carbonate in Part 2 and 3 combined, then the medication will be considered concomitant in Part 2 and 3 combined. Concomitant medications will be listed and summarised by preferred drug name. Concomitant medication usage will be summarised by the number and proportion of subjects receiving each medication within each preferred term for the Safety Analysis Set 2 and the SCS. Multiple medication usage by a subject in the same category will be counted only once. (**Tables 1.3.6 and Table 1.3.7**)

All prior and concomitant medications will be listed (Listing 4.4) including medication name, preferred drug name, the total daily dose (and units), route, frequency, indication, start date of medication, stop date of medication (or whether ongoing), classification of prior and concomitant, and if it was a concomitant medication; whether it was a vitamin D therapy, growth hormone, or proton pump inhibitor.

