**Maximum duration of subject involvement in the study:**

- Planned duration of screening period: Up to 2 weeks if washout not required, otherwise up to 5 weeks
- Planned duration of enrollment period: 64 months
- Planned duration of treatment period: Part 1 - 48 hours, Part 2a - 16 weeks (+ up to 3 weeks for washout between treatments) or Part 2b - 8 weeks, Part 3 - up to 6 months
- Planned duration of follow-up: 7-14 days or  $30 \pm 7$  days in case of kidney transplantation

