#### 5.2 Concomitant Treatment

Concomitant treatment taken between the dates of the first and last dose of investigational product, inclusive, must be listed on the appropriate CRF page.

Treatments not listed in [Table 4](#) above are considered allowable.

Subjects who require treatment with Vitamin D analogues should maintain a stable dose throughout the study unless modification is required due to hypercalcaemia as specified in Section 6.2.1. Vitamin D therapy including dose, unit, route, regimen, indication and dates of use, and the calcium concentration of the dialysate will also be recorded in the CRF.

Treatment with cinacalcet hydrochloride, or with compounds containing phosphate or magnesium, aluminum, or calcium that are used as a phosphate binder are prohibited during the study.

Contraceptives for females should be taken at least 4 weeks prior to enrollment and continued throughout the duration of the study and for 30 days following the last dose of investigational product.

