### **7.1.2 Treatment Period**

#### **7.1.2.1 Part 1: Visit 1.1/ Week -5 to -1 ( $\pm 3$ Days)**

Visit 1.1 should be scheduled on the day after dialysis. See [Table 2](#) for a detailed schedule of assessments for this visit.

- Subjects aged between 10 and 12 years will receive a single dose of 500mg lanthanum (as lanthanum carbonate hydrate) and subjects aged 12 years and over will receive a single 1000mg dose lanthanum (as lanthanum carbonate hydrate; SPD405).
- Blood samples for pharmacokinetic analyses will be taken pre-dose and at 3, 5, 6, 8, 12, 24, and 48 hours after dosing.
- Vital signs (blood pressure and pulse) will be recorded pre-dose, and at 24 and 48 hours after dosing.
- A physical examination will be done at 48 hours post-dose.
- Adverse events and changes to concomitant medication will be recorded.

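### The SAP's Part 1 concomitant-medication rule leaves out drugs started on the dosing day or in the next 2 days, and is unclear for drugs stopped in that window

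*SAP*

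**What the plan says.** SAP Section 9 gives three definitions of concomitant medication.

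- **Part 1:** "any medication with a start date prior to Part 1 and continuing on to 2 days after the day of IP in Part 1". Two conditions are joined by *and*, and nothing covers a drug started during Part 1. The result goes to Table 1.3.3.
- **Part 2:** "any medication with a start date prior to Part 2 and continuing after the first dose of IP in Part 2". An earlier drug therefore need only run past the first dose. A second limb takes in drugs begun during dosing: "or with a start date between the dates of the first and last doses of IP in Part 2, inclusive". Drugs started after the last Part 2 dose are expressly excluded.
- **Parts 2 and 3 combined:** the same structure, including "or with a start date between the dates of the first and last doses of lanthanum carbonate (inclusive) within Part 2 and 3 combined".

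The same section defines a prior medication for each Part by its start date alone: it must begin before the first intake in that Part, and the stop date is irrelevant.

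Protocol 5.2 says: "Concomitant treatment taken between the dates of the first and last dose of investigational product, inclusive, must be listed on the appropriate CRF page". It sets no start-date or persistence condition. Protocol 9.9 plans a summary of medications concomitant to lanthanum in Part 1 but gives no date rule.

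Part 1 is a single dose followed for two days: "Planned duration of treatment period: Part 1 - 48 hours". Sampling covers the same span: "Blood samples for pharmacokinetic analyses will be taken pre-dose and at 3, 5, 6, 8, 12, 24, and 48 hours after dosing". Protocol Table 2 has concomitant medications recorded at every time point to 48 hours, and Section 7.1.2.1 has changes recorded.

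**The concern.** A table of medications concomitant to a single dose should show what subjects were taking around that dose. The Part 1 rule selects instead for long-running drugs: those begun beforehand and, on the natural reading, still in use two days later. A drug given for the first time on the dosing day, or to treat an event in the next 48 hours, fails the first condition however it is read.

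The other two definitions in the section are built differently, and no reason is given for treating Part 1 otherwise. This looks like a drafting slip. The narrower rule is not mentioned in SAP 12.7 or SAP 17.

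At stake is whether Table 1.3.3 is a complete account of medication around the dose, and whether Listing 4.4 flags those drugs correctly. The listing identifies vitamin D, growth hormone and proton pump inhibitors only for drugs classed as concomitant, so a wrong class carries through to that indicator.

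**Working it through.** The plan states no figure to reproduce and no arithmetic is needed. The check applies each rule to test cases. The dosing day is day 0, and Part 1 follow-up ends at day +2.

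| Case | SAP Part 1 rule (Table 1.3.3) | Protocol 5.2, applied to Part 1 alone | SAP Part 2 wording carried over to Part 1 | Part 1 prior (Table 1.3.1) |
|---|---|---|---|---|
| A. Started day −30, ongoing | Counted | Concomitant | Concomitant | Yes |
| B. Started day −30, stopped day +1 | Out, if the rule means still in use on day +2 | Concomitant | Concomitant | Yes |
| C. Started day −30, last taken day 0 | Out, on the same reading | Concomitant | Unclear: stops on the day of the first dose | Yes |
| D. Started day 0 | Out | Concomitant | Concomitant | No |
| E. Started day +1 or +2 | Out | Not covered | Not covered: starts after the last dose | No |

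1. **Drugs started in the window (D, E).** The start is not before Part 1 on any reading, so these drugs are out of Table 1.3.3. The start is not before the first intake either, so they are out of Table 1.3.1. If the subject goes on to Part 2, they meet the prior definition there (Table 1.3.2).

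2. **Drugs stopped in the window (B, C).** These are out only if the second condition requires use on day +2. The wording could also be a loose marker of the end of the window. A drug stopped on day +2 itself could be counted even on the strict reading. All of these drugs stay in Table 1.3.1.

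3. **Which comparator covers which day.** Part 1 has one dose, so its first and last dose dates coincide. The Protocol 5.2 window therefore shrinks to day 0, and so does the started-during part of the Part 2 wording. The conflict with 5.2 holds for B, C and D. The conflict with the SAP's other definitions over drugs started during treatment holds for D. For E, the inconsistency is with the SAP's own reach to 2 days after dosing and with the protocol's collection of medication data to 48 hours.

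4. **Partial dates.** Under SAP 18.5.1, a start date with a missing day in the month of first dose, or a missing day and month in the year of first dose, is normally set to the first-dose date. That turns the drug into case D. A drug that in fact began earlier and is still in use would then appear in neither Part 1 table. Section 9 has a partial-date provision for Part 2 and for Parts 2 and 3 combined, but none for Part 1.

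5. **An undefined boundary.** For a drug started between Visit 1.0 and dosing, the outcome depends on whether Part 1 begins at screening or at the dose. The definition does not say.

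**The case against.** The best defence is that little is hidden. Drugs stopped in the window are in Table 1.3.1. Drugs started in it are prior medications for Part 2 in subjects who continue, and Part 1 subjects are planned to enter Part 2. Listing 4.4 gives start date, stop date and indication, so with so few subjects a reader can see the timing directly. This stands, and it limits the point to one table and one classification. It does not make Table 1.3.3 right: a reader who relies on the table alone would be misled.

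A second defence is that Protocol 5.2 is an instruction on what to record in the CRF, and that Protocol 9.9 gives no date rule. Calling the SAP rule an undeclared change to a protocol analysis is therefore arguable, and the point does not rest on it. The SAP is still inconsistent with its own definitions and with the data collected.

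A reader might infer that the Part 1 pharmacokinetics are compromised, since these drugs are the ones taken around the dose. The documents do not support that. Membership of Pharmacokinetic Set 1 turns on a measurable concentration and on vomiting, and the non-compartmental parameters take nothing from Table 1.3.3. Adverse events, including vomiting, are recorded separately through Visit 1.1.

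A reader might also infer that Protocol 5.2 is contradicted for the whole 48 hours, or that every drug stopped in that time is certainly omitted. Neither follows, for the reasons in steps 2 and 3 of the working.

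**Conclusion.** The definition is wrong as written, and the consequence is minor. The part about drugs started on or after the dosing day holds on any reading. The part about drugs stopped before day +2 assumes that the second condition means still in use on that day.

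The effect is limited to Table 1.3.3 and the prior/concomitant classification in Listing 4.4. No PK parameter, PK-set membership or efficacy result depends on it.

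The number of affected subjects cannot be derived from the documents. One subject would be 1/8 = 12.5% of the planned minimum of 8, or 1/10 = 10% of the first 10 subjects covered by the interim report. Those figures show how much one subject weighs in a small table. They should not be read as an estimate of how often the problem occurs.

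**What to change.** Replace the Part 1 sentence in SAP Section 9 with: a Part 1 concomitant medication is any medication taken at least once from the day of Part 1 dosing through 2 days after, that is, started on or before day +2 and not stopped before day 0. Add a sentence applying the same window to partial dates, so that a start date imputed to the dosing day is counted. Stating the window in days from the dose also removes the uncertainty over when Part 1 begins.

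Copying the Part 2 wording would not be enough. With the first and last dose of Part 1 on the same day, it would still miss drugs started on day +1 or +2.

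The cost is two sentences in the SAP, a re-run of Table 1.3.3 and an update of the classification flag in Listing 4.4. The protocol already has medications recorded through 48 hours, so no new data collection is needed.

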## 10. EFFICACY ANALYSES

Efficacy analyses will be based on the PP2, PP1 and FAS Sets. Generally, Baseline, for all efficacy analyses, is defined as the last assessment prior to the first dose of IP. A detailed description of Baseline, for the study, for treatment groups in Parts 2 and 3, can be found in the TLG shells, Appendix 2.

All confidence intervals will be 2-sided 95% confidence intervals.

### 10.1 Primary Efficacy Endpoint(s) and Analysis

The primary efficacy variable for the study is the percentage of subjects achieving age specific KDOQI targets for serum phosphate level following 8 weeks of lanthanum carbonate treatment. The KDOQI serum phosphorus targets are defined as:

- Adolescents aged  $\geq 12$ - $<18$  years:  $\leq 5.5$ mg/dL (1.78mmol/L)
- Children aged 10 years - $<12$  years:  $\leq 6.0$ mg/dL (1.94mmol/L)

For the primary endpoint, the percentage of subjects achieving age-specific KDOQI targets for serum phosphate levels after 8 weeks of lanthanum carbonate treatment will be descriptively summarized and calculated along with an exact (Clopper-Pearson) 95% confidence interval. PP2 will be the primary analysis population and will be used for this descriptive summarization. Serum phosphate levels tested at a central laboratory will be used for the analysis. In the case of missing central laboratory data, local laboratory data will be used. Please note that serum phosphorous assessments must come from a homogeneous source ie, from either central or local laboratory for baseline and following weeks 8 of lanthanum treatment, respectively, within subject (**Table 3.1.1.1 and Table 3.1.1.2**). KDOQI Serum Phosphorous Target Achievement will be listed (**Listing 6.1**).

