**7.1.2.7 Part 2b: Visits 2.1-2.3 (Weeks 2, 4, and 6; Nominally;  $\pm 3$  Days)**

- Subjects will attend the clinic every 2 weeks for scheduled study visits, starting from the first dose of investigational product.
- At Visit 2.2 only, blood samples will be taken to measure lanthanum pharmacokinetics (2 samples to be selected from: 0-2 hours, 2-4 hours, or 4-6 hours). **Note:** If the sampling is not done at Visit 2.2, blood sampling for pharmacokinetics must be taken at an alternative visit during Part 2b.

- Phosphate levels will be measured locally at Visits 2.1, 2.2 and 2.3 only, for titration purposes.
- The investigational product dispensed at the previous visit will be counted, compliance calculated and the container returned to the subject until exhausted. If necessary, a new container of investigational product will be dispensed.
- The dose of lanthanum carbonate will be adjusted and dispensed as required.
- Any AEs that occurred since the last visit will be recorded.
- A review of any concomitant medication taken since the last visit will be undertaken and changes recorded.
- Confirmation of dialysis adequacy and dietary advice will be made.

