## 9.10 Efficacy Analyses

### 9.10.1 Primary Efficacy Variable

The primary efficacy variable for the study is the percentage of subjects achieving age-specific KDOQI targets for serum phosphate level following 8-weeks of lanthanum carbonate treatment. The KDOQI serum phosphorus targets are defined as:

- Adolescents aged  $\geq 12$ -<18 years:  $\leq 5.5$ mg/dL (1.78mmol/L)
- Children aged 10 years -<12 years:  $\leq 6.0$ mg/dL (1.94mmol/L)

For the primary endpoint, the percentage of subjects achieving age-specific KDOQI targets for serum phosphate levels after 8 weeks of lanthanum carbonate treatment will be descriptively summarized and calculated along with a 95% confidence interval. The FAS and PP2 Sets will be used for this descriptive summarization. Serum phosphate levels tested at a central laboratory will be used for the analysis. In the case of missing central laboratory data, local laboratory data will be used.

Handling of missing data rules will be described in the statistical analysis plan.

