#### **4.6 Per-protocol Set 2 (PP2)**

Per-protocol Set 2 is defined as subjects in the Full Analysis Set who complete 8 weeks of treatment with lanthanum carbonate and who have serum phosphate assessment data available to allow summarizing the percentage of subjects achieving age-specific KDOQI target. Subjects who have serum phosphate levels above the age-specific KDOQI targets prior to the start of lanthanum carbonate treatment will be included in this set. Further details are described in the Evaluable Subjects Determination Plan which can be found in Section 21.

Subjects who experienced hypophosphatemia, that lead to temporary interruption or discontinuation of treatment before the 8-week phosphate assessment, are considered compliant with the 8 week treatment requirement (as treatment dosed per-protocol, Section 6.2.1) and can thus be included in the PP2, PP1, and SCS analysis populations.

In previous versions of the protocol, a Per-protocol (PP) Set, defined as consisting "... of all Subjects in the FAS who complete Part 2 (ie, subjects who have a visit 2.8 serum phosphorus assessment) and do not have any pre-defined major protocol deviations that may affect the primary efficacy variable" was the only analysis set created to summarize efficacy endpoints. Following Protocol Version 6.0 (Amendment 5), two PP sets: PP1 and PP2 were defined.

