## 21. APPENDIX

### 21.1 Evaluable Subject Determination Plan

#### 1. Definition of Evaluable Subject in Per-Protocol Analysis Set 2 for Primary Endpoint Assessment

For the purposes of the primary endpoint assessment, at least 32 subjects, who complete 8 weeks of treatment with lanthanum carbonate and are assessable for baseline and 8 weeks serum phosphate level, will be required. Approximately 65 subjects may be enrolled to acquire at least 32 evaluable subjects. In order to prevent over enrolment, subjects' evaluability status will be assessed and confirmation of achieving at least 32 evaluable subjects will be performed.

The criteria that subjects must meet to determine eligibility include:

- Aged 10 years to <18 years of age at the time of consent
- Confirmed serum phosphorus level drawn prior to commencing Lanthanum therapy in Part 2 or Part 3 of the clinical trial (Baseline Phosphorus)
  - Subjects who participated in Part 2a and received calcium carbonate, baseline serum phosphorus must be drawn after a washout period of up to 3 weeks
- Baseline serum phosphorus levels above KDOQI recommendations:
  - Age <12 years: Serum phosphorus >6.0mg/dL (1.94mmol/L)
  - Age ≥12 years and older: Serum phosphorus >5.5mg/dL (1.78mmol/L)
- Demonstration of 8 weeks of Lanthanum therapy
- Confirmed serum phosphorus level after 8 weeks of Lanthanum therapy
- Both baseline and 8 weeks serum phosphorus levels are assessed at the same lab (central or local lab)
- Subjects, who received lanthanum carbonate therapy in part 2 or part 3 but did not receive 8 weeks of continuous treatment because of temporary dose interruption due to hypophosphatemia (protocol Appendix 2: guidelines for phosphorus and calcium levels), will be considered evaluable, if they satisfy other criteria mentioned above (eg baseline phosphate > KDOQI target).

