## IV. Post 8-week Phosphate Level:

- i) Subset week 8 central lab data from Part 2 or Part 3 central lab data, selecting the on-treatment record closest to target day 56/week 8 (with +/-7 days window). Target day is created using the first dose of Lanthanum in Part 2 or Part 3 (if Part 2 first Lanthanum dose is missing).
- ii) Subset week 8 local lab data from Part 2 or Part 3 local lab data, select the on-treatment record closest to target day 56/week 8 (with +/-7 days window). Target day is created using the first dose of Lanthanum in Part 2 or Part 3 (if Part 2 first Lanthanum dose is missing).
- iii) For subjects who experienced hypophosphatemia, that lead to temporary interruption or discontinuation of treatment before the 8 weeks phosphate assessment they will be considered compliant with the 8 weeks treatment requirement.

In the case of missing central lab data, local lab data will be used. Serum phosphorous assessments must come from a homogeneous source ie, from either central or local lab for baseline and following weeks 8 of lanthanum treatment, respectively, within subject.

If baseline phosphorus value from central lab is available and above the KDOQI criteria, but the central lab 8-week value is missing, then local lab data (baseline and day 56/week 8 phosphorus results) can be used.

NB. Both the baseline and day 56/week 8 phosphorus results must come from a single source (both central or both local).

If baseline phosphorus value from central lab is available and not above the KDOQI criteria, then the subject is not evaluable even if the subject has local lab values for both baseline and 8-week and the baseline value satisfies KDOQI criteria. Evaluability based on local lab is assessed only if central laboratory data is missing.

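### The same-laboratory rule can discard a valid Week 8 result from the primary responder tables, and the baseline selection can wrongly exclude Part 2b subjects who had a washout

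*SAP*

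**What the plan says.** The primary variable in SAP 10.1 is "the percentage of subjects achieving age specific KDOQI targets for serum phosphate level following 8 weeks of lanthanum carbonate treatment", judged against an age-specific threshold. On the population, SAP 10.1 states that "PP2 will be the primary analysis population and will be used for this descriptive summarization"; the SAP table list adds an FAS version (Table 3.1.1.2).

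On the source of the value, Protocol 9.10.1 has a simple fallback: "In the case of missing central laboratory data, local laboratory data will be used". It then leaves missing-data rules to the SAP. SAP 10.1 repeats the fallback and attaches a condition for both primary tables: "serum phosphorous assessments must come from a homogeneous source ie, from either central or local laboratory for baseline and following weeks 8". SAP 21.1 turns this into a PP2 evaluability criterion: "Both baseline and 8 weeks serum phosphorus levels are assessed at the same lab (central or local lab".

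On baseline, SAP 4.6 limits PP2 to "Subjects who have serum phosphate levels above the age-specific KDOQI targets prior to the start of lanthanum carbonate treatment". SAP 4.4 sets no baseline condition for the FAS. SAP 21.1 (III) takes the central baseline closest to the first lanthanum dose. SAP 21.1 (IV) adds that a central baseline not above target makes the subject non-evaluable, even if the local baseline qualifies and a local Week 8 value exists.

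On the Week 8 value, SAP 21.1 (IV) tells the programmer, for local data, to "select the on-treatment record closest to target day 56/week 8 (with +/-7 days window". For Part 2b, Protocol 7.1.2.7 says "Phosphate levels will be measured locally at Visits 2.1, 2.2 and 2.3 only, for titration purposes". Protocol 7.1.2.5 has the matching restriction to Visits 2.5-2.7 for lanthanum treatment in Part 2a.

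**The concern.** Two separate mechanisms can remove a subject whose Week 8 answer is known.

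**Mixed sources.** Treatment may start on a local result (Protocol 7.1.1.3, 7.1.1.4, 7.1.2.3, 7.1.2.4). Suppose the local baseline qualifies, no usable central baseline exists, and the central Week 8 value is present. The rule then requires a local Week 8 value. If there is none, the subject drops out, although the central Week 8 value classifies response completely.

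**Pre-washout baseline.** A Part 2b subject enters washout because phosphate at Visit 1.0 is too low. If the central confirmation at W1 is missing, the closest central value is the one from Visit 1.0. SAP 21.1 then rejects the subject for a baseline not above target, although enrolment was valid. The SAP 21.1 requirement for a post-washout baseline is written only for Part 2a subjects who received calcium carbonate.

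At stake is a primary set that the SAP has already reduced from 35 to 32 after severe recruitment difficulty. Losses of this kind depend on laboratory logistics and not on treatment or outcome definition.

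**Working it through.** **The plan's own figure.** The SAP justifies 32 evaluable subjects by the chance of seeing at least one event with a true rate of 5%: 1 − 0.95^32 = 0.806, which matches the stated 80.6%. The plan gives no figure for how many subjects have mixed sources.

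**Visit timing against the Week 8 window.** The window is day 56 ± 7, that is days 49-63 from the first lanthanum dose (SAP 21.1, IV). Visit windows are ±3 days in Part 2 and ±1 week in Part 3 (Tables 1 and 3).

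| Route | Visit | Days on lanthanum | Local phosphate scheduled? | In window? |
|---|---|---|---|---|
| Part 2b | 2.3 | 42 ± 3 = 39-45 | yes | no |
| Part 2b | 2.4 | 56 ± 3 = 53-59 | no | yes |
| Part 2b | 3.0 | 84 ± 7 = 77-91 | yes | no |
| Part 2a, lanthanum | 2.7 | 39-45 | yes | no |
| Part 2a, lanthanum | 2.8 | 53-59 | no | yes |
| Part 2a, lanthanum | 3.0 | 77-91 | yes | no |
| First lanthanum dose in Part 3 | 3.1 | 56 ± 7 = 49-63 | yes | yes |

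The last row is an inference: it counts monthly visits from the start of Part 3. On the two Part 2 routes, no scheduled local sample falls in the window.

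**Who is lost, on a Part 2 route with no unscheduled local sample.**

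- Central baseline and central Week 8 present, baseline post-washout where relevant: kept.
- No central baseline, qualifying local baseline, central Week 8 present: lost because of the rule.
- Part 2b with washout, W1 central confirmation missing, Visit 1.0 central value not above target: lost through baseline selection, whatever the Week 8 source.
- Central Week 8 missing: lost with or without the rule, because no local value is scheduled.

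The second and third cases cannot be the same subject, since one needs the central baseline to be absent and the other needs it to be present. Their remedies are linked, however. If only the baseline selection were corrected, the third subject would have a local post-washout baseline and a central Week 8 value, and the same-laboratory rule would then remove that subject.

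**Size.** Each lost subject is 1/32 = 3.1% of the target. The loss of 4 and a response rate near 60% are assumptions. Exact (Clopper-Pearson) 95% intervals:

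- 19/32 = 59%: 40.6% to 76.3%, width 35.7 points.
- 17/28 = 61%: 40.6% to 78.5%, width 37.9 points.

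The estimate can move more than the width. Starting from 16/32 = 50%, dropping 1 subject gives 15/31 to 16/31 (48-52%), dropping 3 gives 13/29 to 16/29 (45-55%), and dropping 6 gives 10/26 to 16/26 (38-62%), depending on who is dropped.

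**Consistency within SAP 21.1.** The criteria in its section 1 and the text under IV include the same-laboratory condition. The shorter list of conditions in its section 1.2 does not. Two programmers could build different PP2 sets.

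**The case against.** The strongest defence is that one source on both sides of a hard threshold is a reasoned choice. The protocol itself expects central and local results to disagree at times, and PP2 does need a baseline above target. That stands as far as it goes: a reader might infer that baseline is irrelevant to the primary analysis, and for PP2 entry it is not. But PP2 needs a qualifying baseline, not one from the laboratory that supplied the Week 8 value, and the FAS definition needs none.

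A reader might also infer that the SAP silently departs from the protocol, since Section 17 does not list the condition. The documents do not clearly support this. Protocol 9.10.1 hands missing-data rules to the SAP, so the condition can be read as delegated detail.

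Another tempting reading is that the local fallback can never work. That is too broad. Subjects first dosed with lanthanum in Part 3 have local Visit 3.1 near Week 8, and unscheduled local samples may exist. Protocol 7.1.2.3 itself mentions local results at Part 2a Visit 2.4, where Table 1 shows no local test.

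The affected group is probably small. Central samples are required at screening and expected at washout. The full baseline definition is in the table shells (Appendix 2), which are not among these documents and may close part of the gap. Evaluability is also monitored, with about 65 enrolments allowed to reach 32, so losses cost enrolment before they cost precision. Finally, Tables 3.1.8.1 and 3.1.8.2 already summarise target achievement by week. The PP2 version inherits the exclusions, and the FAS version does not replace the primary result.

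**Conclusion.** The concern holds in a limited form. For response, the same-laboratory rule can discard a valid central Week 8 value for no analytic gain, and on the Part 2a lanthanum and Part 2b routes no scheduled local sample can rescue the subject. Independently, the baseline selection can exclude a validly enrolled Part 2b subject on a pre-washout value.

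The number affected is unknown and probably small. With an assumed loss of 4 from 32, the interval widens by about 2 points. The endpoint is descriptive, so no test or error rate is at risk. The conclusion assumes that visits follow the schedule and that the unseen table shells do not already settle baseline selection. It does not show that the target of 32 will be missed, or that the reported percentage will be biased in a known direction.

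**What to change.** Amend SAP 10.1 and 21.1 before database lock:

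- For the responder endpoint, use the central Week 8 value, otherwise the local one, whatever the source of the baseline.
- For PP2 entry, use the last pre-lanthanum value, central if present and otherwise local. In anyone who had a washout, including Part 2b, accept only a post-washout value.
- Confine the same-laboratory rule to change-from-baseline tables, which is the case SAP 10.3 uses to illustrate it.
- Add a same-laboratory sensitivity table for the responder endpoint.
- Bring the condition list in section 1.2 of SAP 21.1 into line with the criteria in its section 1 and the text under IV. State how a subject without a usable Week 8 value counts in the FAS denominator, since SAP 18.2 gives no rule.
- Record the final rule in Section 17, for transparency.

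The cost is SAP wording and one extra table. The downside is that a few subjects will have baseline and Week 8 from different laboratories; the sensitivity table shows whether that matters. The change does not recover Part 2 subjects with no central Week 8 value. That would need a local sample at the Week 8 visit, which is a protocol matter. Label: cheap improvement.
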